6.3 Dose Modifications for Infusion-Related Reactions and Cytokine Release Syndrome

The mechanism of action of flotetuzumab is the creation of an immunological synapse between the leukemic blast bearing CD123 and T cells, leading to T cell activation and killing of the leukemic cell. Activation of T cells is associated with the elaboration of various cytokines including IFN- γ , TNF- α , IL-2, IL-6, IL-4 and IL-10. This T cell activation and subsequent cytokine production can lead to infusion related reactions (IRRs) or cytokine release syndrome (CRS).

Patients should be monitored closely for the development of IRRs during flotetuzumab infusion. Medications and supportive measures for the treatment of such reactions should be available for immediate use for an infusion reaction during study drug administration and may include, but are not limited to: subcutaneous epinephrine, antihistamines, corticosteroids, IV fluids, vasopressors, oxygen, bronchodilators, and antipyretics. Resuscitation equipment and other supplies for the emergency management of an allergic/toxic reaction must be available. The patient should be treated according to the best available local practices and procedures. All supportive measures consistent with optimal patient care will be provided throughout the study according to institutional standards.

If possible, a serum sample should be obtained at the time of diagnosis of CRS for evaluation of circulating cytokines. Follow-up samples should also be obtained at the time of resolution of symptoms. Application of appropriate diagnostic or treatment procedures should not be delayed or hindered to obtain such samples.

Other types of adverse reactions may be observed during infusion that are not interpreted as related to cytokine release, but may be related to flotetuzumab. Such reactions should be diagnosed, graded and managed according to best practices. Early and frequent consultation with the study medical monitor is encouraged.

6.3.1 CRS Management

The following are treatment guidelines (which may be modified as needed by the responsible investigator according to the best practices of medicine) for CRS related to flotetuzumab. Early intervention at the first signs of CRS, including pyrexia, tachycardia, tachypnea and/or hypotension in the absence of alternative etiologies and in consistent temporal relationship to administration of flotetuzumab, should be undertaken.

CRS is a commonly observed event during treatment with flotetuzumab based on experience in the adult population, with the majority of patients experiencing at least 1 event of Grade 1 or 2. Based on current understanding gained from patients treated with blinatumomab and CAR T cells, CRS is likely to be a common toxicity that can be managed through supportive care and anti-cytokine interventions to allow for full activity of T cells during therapy. A consensus grading system for CRS has been proposed by the American Society for Blood and Marrow Transplantation which will be utilized for this study ([Table 1](#)).

Table 1: ASBMT CRS Consensus Grading

CRS Parameter	Grade 1	Grade 2	Grade 3	Grade 4
Fever*	Temperature \geq 38°C	Temperature \geq 38°C	Temperature \geq 38°C	Temperature \geq 38°C
		With		
Hypotension	None	Not requiring vasopressors	Requiring a vasopressor with or without vasopressin	Requiring multiple vasopressors (excluding vasopressin)
		And/or [#]		
Hypoxia	None	Requiring low-flow nasal cannula ^{#@} or blow-by supplemental oxygen	Requiring high-flow nasal cannula ^{#@} , facemask, non-rebreather mask, or Venturi mask supplemental oxygen	Requiring positive pressure (e.g., CPAP, BiPAP, intubation and mechanical ventilation)

Organ toxicities associated with CRS may be graded according to CTCAE v5.0 but they do not influence CRS grading.

*Fever is defined as temperature \geq 38°C not attributable to any other cause. In patients who have CRS then receive antipyretic or anticytokine therapy such as tocilizumab or steroids, fever is no longer required to grade subsequent CRS severity. In this case, CRS grading is driven by hypotension and/or hypoxia.

[#]CRS grade is determined by the more severe event: hypotension or hypoxia not attributable to any other cause. For example, a patient with temperature of 39.5°C, hypotension requiring 1 vasopressor, and hypoxia requiring low-flow nasal cannula is classified as grade 3 CRS.

[@]Low-flow nasal cannula is defined as oxygen delivered at \leq 6 L/minute. Low flow also includes blow-by oxygen delivery, sometimes used in pediatrics. High-flow nasal cannula is defined as oxygen delivered at $>$ 6 L/minute.

Source: Lee et al., 2018³⁶

THIS PROTOCOL IS FOR RESEARCH PURPOSES ONLY, SEE PAGE 1 FOR USAGE POLICY

CRS should be managed as described below. Every attempt should be made to continue the infusion during management of the reaction.

6.3.1.1 Grade 1 Infusion Reactions, Including CRS and IRR:

- Slow the infusion rate by 20%;
- Monitor the patient for worsening of condition;
- Administer IV fluids, diphenhydramine IV, acetaminophen PO/IV for fever, and oxygen and bronchodilators for mild bronchospasm, as appropriate;
- Administer tocilizumab (4-8 mg/kg [max 800 mg/dose] IV) for Grade 1 IRR/CRS that does not resolve within 2 hours with supportive therapy, or is associated with any of the following signs and symptoms:
 - Temperature > 101.5°F (38.6°C)
 - Signs of pending respiratory compromise as indicated by RR > 20/min or pulse oximetry < 93% in the absence of supplemental oxygen
 - Decreases in diastolic or systolic BP to < 15 mmHg below pretreatment baseline
 - HR > 20 bpm above pre-treatment baseline
 - Note: isolated changes in hemodynamic parameters alone without pulmonary compromise or fever should not prompt immediate use of tocilizumab.
- Corticosteroids should not be used for Grade 1 IRR/CRS.
- Continue rate at 20% reduction and increase infusion rate to the original rate by increasing the infusion rate after stabilization or resolution of symptoms, as tolerated. If multiple dose reductions are required or if a more gradual increase in the rate of infusion is desired, dose increasing must be discussed with the study chair.

6.3.1.2 Grade 2 Infusion Reactions and Infusion-Related Events:

- Slow the infusion rate by 50%;
- Administer IV fluids, diphenhydramine IV, acetaminophen PO/IV for fever, and oxygen and bronchodilators for bronchospasm, as appropriate and if not administered previously;
- Tocilizumab should be used for Grade 2 IRR/CRS that does not resolve with other measures within 2 hours, or that requires the use of supplemental oxygen > 4L by nasal cannula or low dose vasopressors.
 - Tocilizumab Dosing:
 - < 30 kg: 12 mg/kg
 - ≥ 30 kg: 8 mg/kg [max 800 mg]

THIS PROTOCOL IS FOR RESEARCH PURPOSES ONLY, SEE PAGE 1 FOR USAGE POLICY

- In patients with CRS who respond to tocilizumab, fever and hypotension often resolve within 6 hours, and pressors and other supportive care measures can be weaned quickly thereafter. In some cases, however, symptoms may not completely resolve, and continued aggressive support may be necessary for several days. If the patient's condition does not improve or stabilize within 8 – 12 hours of the tocilizumab dose, administration of a second dose of tocilizumab and/or a second immunosuppressive agent, such as additional dexamethasone, should be considered. Tocilizumab is generally not used in the management of CNS symptoms without significant hemodynamic instability or other life-threatening symptomatology.
- Corticosteroids may be used for Grade 2 IRR/CRS that does not respond to other measures, including tocilizumab. Dexamethasone is the corticosteroid of choice administered at a total daily dose of at least 0.2 – 0.4 mg/kg/day (maximum 24 mg per day, in addition to dexamethasone administered during daily dose escalation) administered preferably intravenously divided 3 – 4 times daily for at least 1 day but no more than 4 days. The dose should be stopped or tapered as clinically indicated.
- Continue rate at 50% reduction and increase infusion rate to the original rate by doubling the infusion rate after stabilization or resolution of symptoms, as tolerated. If multiple dose reductions are required or if a more gradual increase in the rate of infusion is desired, dose increasing must be discussed with the study chair.
- Monitor for worsening condition.

6.3.1.3 Grade 3 Infusion Reactions and Infusion-Related Events:

- Stop the infusion,
- TO AVOID EXACERBATION OF INFUSION REACTION OR CRS: DO NOT FLUSH THE TUBING – ASPIRATE RESIDUAL DRUG FROM THE PORT LUMEN;
- Administer IV fluids, diphenhydramine IV, acetaminophen PO/IV for fever, and oxygen and bronchodilators for mild bronchospasm, as appropriate.
- Provide appropriate circulatory support including vasopressors as medically indicated;
- Administer tocilizumab if not administered previously. If administered previously, an additional dose may be used for prolonged or recurrent episodes.

THIS PROTOCOL IS FOR RESEARCH PURPOSES ONLY, SEE PAGE 1 FOR USAGE POLICY

- Grade 3 CRS that is refractory to tocilizumab should be treated with corticosteroids. Dexamethasone is the corticosteroid of choice administered at a total daily dose of at least 0.2 – 0.4 mg/kg/day (maximum 24 mg per day) administered preferably intravenously divided 3 – 4 times daily for at least 1 day but no more than 4 days. The dose should be stopped or tapered as clinically indicated.
- If infusion reaction improves to \leq grade 2 within 72 hours, infusion may be resumed at no greater than 50% of the original rate once symptoms decrease to Grade 1. The rate may then be escalated to the original rate after 30 minutes, as tolerated. A more gradual increase in the rate of infusion may be undertaken after consultation with the study chair;
- If infusion reaction DOES NOT improve to \leq grade 2 within 72 hours or if there are multiple grade 3 infusion reactions, flotetuzumab treatment must be permanently discontinued:
 - Report as an immediately reportable event (IRE) immediately;
 - Report the event as a serious adverse event (SAE) if appropriate.

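### The blood-pressure trigger for tocilizumab in Grade 1 reactions has two opposite readings, and the Grade 1 list is not aligned with the study's own CRS grading table

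*Combined protocol and SAP*

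**What the plan says.** Section 6.3.1.1, titled "Grade 1 Infusion Reactions, Including CRS and IRR", directs tocilizumab "for Grade 1 IRR/CRS that does not resolve within 2 hours with supportive therapy, or is associated with any of the following signs and symptoms". The signs are a temperature above 38.6°C, a respiratory rate above 20/min or oximetry below 93% off oxygen, the blood-pressure line "Decreases in diastolic or systolic BP to < 15 mmHg below pretreatment baseline", and "HR > 20 bpm above pre-treatment baseline". A note under the list adds that "isolated changes in hemodynamic parameters alone without pulmonary compromise or fever should not prompt immediate use of tocilizumab".

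Table 1 in 6.3.1 grades CRS. Every grade carries a temperature of at least 38°C. The hypotension row begins "Hypotension None Not requiring vasopressors", that is, none at Grade 1 and hypotension without vasopressors at Grade 2; needing a vasopressor is Grade 3. Hypoxia is also absent at Grade 1. The footnotes say that "CRS grade is determined by the more severe event: hypotension or hypoxia not attributable to any other cause", and that fever is no longer required for grading once a patient with CRS has had antipyretic or anticytokine treatment.

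Section 6.3.1.2 gives the Grade 2 rule: "Tocilizumab should be used for Grade 2 IRR/CRS that does not resolve with other measures within 2 hours", or that needs more than 4 L of oxygen by nasal cannula or low-dose vasopressor support.

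**The concern.** Tocilizumab is the first anti-cytokine drug named in each of the Grade 1 to 3 instructions, and 6.3.1.1 is where a site first decides whether to give it. If the blood-pressure line can be read in opposite directions, two sites following the same text may act differently on the same child. If the listed signs also straddle two grades, the choice of grade changes the timing, the printed dose, the infusion rate and the steroid rule together. Rescue use and recorded CRS severity are part of what this safety study describes, so inconsistent rescue bears on patient safety and on how readable the toxicity data are.

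**Working it through.** No sample size, error rate or stated figure is involved. The check is a truth table for one sentence, followed by a comparison of passages.

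**1. The blood-pressure line.** Let P be the baseline and d > 0 the fall, so current pressure is P − d.

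- Reading A, size of the fall: trigger if d < 15.
- Reading B, level reached: trigger if P − d < P − 15, that is, if d > 15.

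P cancels, so the baseline does not matter. With assumed baselines of 90 and 110 mmHg, Reading B requires pressure below 75 and below 95 respectively.

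| Fall d (mmHg) | Reading A | Reading B |
|---|---|---|
| 1, 5, 10, 14 | trigger | no trigger |
| 15 | no trigger | no trigger |
| 16, 20, 30, 40 | no trigger | trigger |

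The readings agree only at d = 15. The heart-rate line has one reading: rate above baseline + 20. From an assumed baseline of 100, a rise of 20 does not trigger and a rise of 21 does.

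**2. Grade 1 against Grade 2.**

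| Item | Grade 1 (6.3.1.1) | Grade 2 (6.3.1.2) |
|---|---|---|
| Infusion slowed by | 20% | 50% |
| Tocilizumab given | on any listed sign, or if unresolved at 2 h | if unresolved at 2 h, or oxygen > 4 L, or low-dose vasopressors |
| Printed tocilizumab dose | 4–8 mg/kg, max 800 mg | 12 mg/kg under 30 kg; 8 mg/kg from 30 kg, max 800 mg |
| Corticosteroids | not to be used | may be used if other measures, including tocilizumab, fail |

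Take a febrile child with a blood-pressure fall that meets the Grade 1 sign. Called Grade 1, the event triggers tocilizumab at once. If the same fall is judged to be hypotension not needing vasopressors, Table 1 makes the event Grade 2, and on that sign alone the rule waits 2 hours. Oximetry behaves similarly: below 93% off oxygen is an immediate Grade 1 trigger, but the same child on low-flow oxygen at 4 L or less is Grade 2 with no immediate trigger.

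The printed doses cannot agree below 30 kg. Eligibility starts at 17 kg (4.1.2), so this concerns children from 17 kg to under 30 kg. From 30 kg, the Grade 2 figure is the top of the Grade 1 range.

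**3. Vasopressors.** The Grade 2 rule includes low-dose vasopressor support. Table 1 puts a vasopressor requirement at Grade 3, where 6.3.1.3 stops the infusion instead of slowing it by 50%. For CRS these passages conflict.

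**4. The note.** It covers hemodynamic change without pulmonary compromise or fever. At initial grading Table 1 requires at least 38°C for Grade 1 CRS, so the note cannot apply there. It reaches only afebrile infusion reactions that are not CRS, or CRS after antipyretic or anticytokine treatment.

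**The case against.** The strongest reply is that the line is not reversed. The word before the inequality can introduce a level reached, and Reading B then has the same structure as the heart-rate line beside it. That stands: a reader might infer that the inequality is printed backwards, but the text supports two readings and does not settle which was meant.

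A reader might also infer that a child with a large fall gets no rescue. The documents do not support that. Even under Reading A, tocilizumab is reached through non-resolution at 2 hours or any other listed sign. A fall judged to be hypotension moves CRS to the Grade 2 rule, and Grade 3 directs tocilizumab if it has not been given. Section 6.3.1 also urges early intervention at first signs, hypotension among them.

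The mismatch with Table 1 is conditional. The table gives no pressure or oximetry cut-off, a fall from baseline need not be hypotension, Grade 2 hypoxia is defined by the oxygen needed, and 6.3.1.1 covers non-CRS reactions that Table 1 does not grade. The note therefore has a use, though a narrow one.

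Finally, 6.3.1 calls these guidelines that the investigator may modify. That lowers the stakes, but a guideline still needs a default that can be read one way.

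**Conclusion.** The blood-pressure trigger is ambiguous, with opposite actions at every fall except exactly 15 mmHg. The Grade 1 list, the Grade 2 rule, the note and Table 1 do not fit together. The ambiguity follows from the sentence alone. The Grade 1/Grade 2 overlap depends on the clinician judging the fall to be hypotension, or on oxygen being started. The vasopressor conflict holds for any CRS event graded by Table 1. This is a drafting fault worth correcting at the next amendment; it does not undermine the design.

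Two inferences about size should be resisted. Section 2.3.1 reports Grade 1 CRS in 25.8% and Grade 2 in 58.1% of adults, and 25.8% + 58.1% = 83.9% might be taken as the share affected. That sum counts adults by CRS grade, not patients in whom the blood-pressure line decides treatment; the documents give no such count. Nor do they link this line to dose-limiting toxicity counts. The 72-hour exemption in 5.5.1.1 concerns Grade 3 events, for which tocilizumab is directed separately. Sites may differ in rescue use; the documents do not show that they will.

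**What to change.** Reword the blood-pressure line in 6.3.1.1 so that its direction has only one reading. Reconcile the Grade 1 and Grade 2 tocilizumab triggers, including the oximetry sign and the vasopressor wording, with Table 1, so that each sign maps to one grade and one set of actions. State which reactions the note covers: non-CRS reactions, CRS after treatment of fever, or febrile Grade 1 CRS as well. All thresholds and doses are for the sponsor's clinical team to set; none is proposed here. The cost is a wording amendment to a few lines in 6.3.1 and a notice to sites, with no new procedures or data collection.

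### For CRS, the Grade 2 tocilizumab trigger in 6.3.1.2 assumes vasopressor use that Table 1 grades as 3

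*Combined protocol and SAP*

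**What the plan says.** Section 6.3.1 adopts the ASBMT consensus grading for CRS, "which will be utilized for this study", and prints it as Table 1. The hypotension row reads:

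- Grade 2: "Not requiring vasopressors"
- Grade 3: "Requiring a vasopressor with or without vasopressin"
- Grade 4: "Requiring multiple vasopressors (excluding vasopressin")

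No row carries a dose threshold. A Table 1 footnote gives a worked example: a febrile patient with "hypotension requiring 1 vasopressor, and hypoxia requiring low-flow nasal cannula is classified as grade 3 CRS".

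Management then follows by grade. The Grade 2 section, 6.3.1.2, opens with "Slow the infusion rate by 50" percent. It calls for tocilizumab in Grade 2 IRR/CRS that has not resolved within 2 hours on other measures, or that "requires the use of supplemental oxygen > 4L by nasal cannula or low dose vasopressors". A later bullet in the same section begins "In patients with CRS who respond to tocilizumab, fever and hypotension often resolve within 6 hours, and pressors" and goes on to say that pressors can then be weaned quickly.

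The Grade 3 section, 6.3.1.3, stops the infusion. It may resume at no more than half the original rate, once symptoms are down to Grade 1. Treatment ends permanently if the reaction has not improved to Grade 2 or lower within 72 hours, or if there are multiple Grade 3 reactions.

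**The concern.** Under Table 1, no CRS event that needs a vasopressor can be Grade 2. The vasopressor half of the 6.3.1.2 trigger therefore describes a CRS patient who cannot exist under the study's own grading. A clinician who opens the Grade 2 section and finds low-dose vasopressors listed may reasonably conclude that such a patient is still Grade 2.

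The grade decides three things: whether the infusion is slowed or stopped, whether the 72-hour limit applies, and whether the episode counts toward permanent discontinuation. Section 2.3.1 reports IRR/CRS as the most common treatment-related event in the adult trial, so these are instructions that sites can expect to use. What is at stake is a child with vasopressor-requiring CRS who continues to receive a T-cell-engaging drug at half rate when the protocol's grading calls for a stop.

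**Working it through.** No sample size, error rate or estimate is involved, so the check is a comparison of texts.

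1. **Which rule sets the CRS grade?** Table 1. Section 6.3.1 adopts it for the study, and section 5.5.1.1 names the same ASBMT grading for the DLT definition.

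2. **What grade does Table 1 give to CRS with one low-dose vasopressor?** Grade 3. The Grade 2 cell excludes vasopressors, the Grade 3 cell covers a single vasopressor without reference to dose, and the footnote example confirms it.

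3. **What does 6.3.1.2 assume?** The trigger names IRR/CRS, not IRR alone, and is worded as a Grade 2 event that requires low-dose vasopressors. For CRS that contradicts step 2.

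4. **Does the oxygen half of the trigger conflict too?** No. Table 1 allows low-flow nasal cannula at Grade 2 and defines low flow as up to 6 L/minute, so a patient above 4 L and up to 6 L can be Grade 2. Only the vasopressor half is wrong.

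5. **What follows from each grade?**

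| | Handled as Grade 2 (6.3.1.2) | Grade 3 (6.3.1.3) |
|---|---|---|
| Infusion | continue at half rate | stop |
| Return to full rate | double the rate after stabilization or resolution | restart at no more than half rate once at Grade 1, then escalate |
| 72-hour limit | none | yes |
| Repeat episodes | no discontinuation rule | multiple Grade 3 reactions end treatment |
| Tocilizumab | yes, by the trigger | yes, if not already given |

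Tocilizumab is available in both columns, so the drug that the trigger calls for does not depend on the grade. The infusion instruction and the discontinuation rules do.

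6. **A separate slip, in 6.3.1.1.** The Grade 1 tocilizumab criteria include a blood pressure decrease to less than 15 mmHg below baseline. Read literally, this captures falls smaller than 15 mmHg. The note in the same list, that isolated hemodynamic changes should not prompt immediate tocilizumab, limits the effect.

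**The case against.** The strongest reply is that there is no real ambiguity. The management sections are entered by grade, Table 1 alone grades CRS, and one vasopressor is Grade 3, so 6.3.1.3 governs. This stands. A reader might infer that the protocol gives two equally valid instructions and no way to choose between them. The documents do not support that. The defect is a line that contradicts the governing table and can mislead a site.

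A second reply is that the trigger has a legitimate use, because 6.3.1.2 also covers non-CRS infusion reactions, which Table 1 does not grade. This also stands, and it is why the point is limited to CRS. It does not rescue the line for CRS, which the trigger names.

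A third reply is that the trigger describes a Grade 2 patient who worsens, and that the bullet on weaning pressors is general tocilizumab prose. The bullet is indeed weak evidence alone, since it also mentions life-threatening symptoms. But the trigger speaks of a Grade 2 event that requires vasopressors, and 6.3.1.3 has its own tocilizumab instruction for the patient who has moved up a grade.

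There are also safeguards. The steps are guidelines that the investigator may modify. Patients stay in hospital through Cycle 1 (5.1). The Study Chair must hear of any dosage modification (6.0), and multiple dose reductions require discussion of re-escalation with the chair (6.3.1.2). Section 6.4.2 asks for interruption to be considered in severe hypotension on vasopressors. These lower the risk, but none corrects the wording. The general request in 6.3.1 to try to keep the infusion running leans toward the less protective reading.

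**Conclusion.** The wording is wrong for CRS and should be corrected. The 6.3.1.2 trigger contradicts Table 1, Table 1 governs, and the patient described belongs in 6.3.1.3. The risk is that a site follows the Grade 2 text, continues at half rate, and does not count the episode toward the Grade 3 discontinuation rule.

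The frequency cannot be derived. The adult figure of Grade 3 or higher events in 4 of 31 patients (2.3.1) does not say how many involved a single low-dose vasopressor.

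Two stronger readings should be resisted. A reader might infer that DLT assessment or dose finding is compromised. It is not, because 5.5.1.1 names ASBMT grading for CRS. A reader might also multiply the half rate by 6 or 72 hours and present the result as excess exposure. Neither is an episode length: 6 hours is when fever and hypotension often resolve after tocilizumab, and 72 hours is the limit for improving to Grade 2 or lower. The difference between half rate and none is real while an episode lasts, but the documents give no duration that would make it a measure of harm.

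The conclusion rests on Table 1 as printed and makes no claim about non-CRS reactions.

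**What to change.** In 6.3.1.2, limit the low-dose vasopressor trigger to non-CRS infusion reactions and add: *CRS requiring any vasopressor is at least Grade 3 by Table 1 and is managed under 6.3.1.3 or 6.3.1.4.*

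The cost is amendment wording, with no added patients, visits or procedures. The downside is that some CRS patients on a low-dose vasopressor whom a site would have slowed will be stopped, and repeat episodes will count toward permanent discontinuation. Table 1 already implies both.

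Separately, and minor: reword the 6.3.1.1 blood pressure criterion as a fall of more than 15 mmHg below pretreatment baseline, and keep the existing note on isolated hemodynamic changes.
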